5 Levels of Significance

No hypotheses are specified for this study and no p-values are being calculated, therefore no level of significance is specified. All estimation of endpoints will be performed using 95% confidence intervals.

6 Analysis Sets

The summary of all performance and safety endpoints will be performed on the set of subjects in whom the ENSEAL X1 device is utilized during the surgical procedure. This will be labeled the ENSEAL Analysis Set. This set of subjects will be identified by having at least one entry in the “Vessel Transected” eCRF or by having answered “Yes” to the question “Was ENSEAL X1 used for tissue cutting or dissection?” on the “ENSEAL X1 Usage” eCRF. The summary of all primary and secondary performance endpoints will be performed by procedure group (thoracic, urologic, and ENT) and on the entire pooled set of subjects. The safety endpoints will be summarized by procedure group and for the entire pooled set of subjects.

7 Sample Size Justification

A sample size of 105 to 120 treated subjects is planned for enrollment in this study. No formal hypothesis is being tested in this study; thus, the sample size was not statistically sized, but rather is considered sufficient for a descriptive summary of performance endpoints within each procedure group. It is expected that at least 1 vessel will be transected within each procedure, providing an expected minimum of at least 35 transections within each procedure group for a total of at least 105 transections.

From a safety perspective on the pooled analysis of 105 subjects and in consideration of rare AEs that may occur (e.g., bleeding requiring blood product transfusion), for an event that has an incidence rate of, for example, 2%, then in a sample of 105 subjects, the probability of observing at least 1 event is 88.0% under a binomial probability model. Thus, this sample size provides a high probability of observing an AE if they do occur and provides reasonable assurance to conclude that

the likelihood of such AEs is less than 3.5% if they do not occur based on the upper limit of an exact 95% confidence interval when 0 events out of 105 subjects are observed.

8 Analyses to be Conducted

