8.4.1 Primary Endpoint and Associated Hypotheses

No formal hypotheses are specified for the primary endpoint of this study.

The primary performance endpoint in this study is the number and percentage of vessels where hemostasis (\leq Grade 3) is achieved using the ENSEAL X1 device. The hemostasis grading scale is defined as:

- Grade 1: no bleeding at transection site;
- Grade 2: minor bleeding at transection site, no intervention needed;
- Grade 3: minor bleeding at transection site, mild intervention needed, use of compression, basic energy devices (monopolar and/or bipolar device), and/or touch-ups with ENSEAL X1.
- Grade 4: significant bleeding (e.g., pulsatile blood flow, venous pooling) requiring intervention such as extensive coagulation or use of additional hemostatic measures (e.g., hemoclips, staples, sutures, fibrin sealants, other advanced energy products).

The primary performance endpoint will be summarized at the vessel transection level as multiple vessel transections per subject are expected; that is, the denominator for the primary endpoint will be the total number of vessel transections and the numerator will be the number of vessel transections where hemostasis (\leq Grade 3) is achieved. An exact 95% confidence interval using the Clopper-Pearson method will be estimated. The statistics for the primary performance endpoint will be presented by procedure group and in total.

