8.8 Sensitivity Analyses

The analysis of the primary performance endpoint described above in Section 8.4.1 makes the assumption of independence of vessel transections within a subject in estimation of variance for the confidence interval calculation. If the percentage of subjects with two or more vessel transections exceeds 10% a sensitivity analysis will be performed to account for the potential dependence among vessel transections within a subject. The 95% confidence interval will be estimated using a bootstrap approach. If the percentage of subjects with two or more vessel transections is less than 10% the bias due to assuming independence is expected to be small, and no sensitivity analysis will be conducted.

Bootstrap process:

For each subject, the outcome of each activation will be represented by a vector of 1's (indicating a score of \leq Grade 3 hemostasis) and 0's (indicating a score of Grade 4 hemostasis). This vector will be re-sampled with replacement to generate a bootstrap sampled vector of observations for each subject. Then, the proportion of observations scored as \leq Grade 3 hemostasis for the bootstrap sample will be calculated. This process will then be repeated a minimum of 5000 times to generate a sampling distribution for the proportion of activations achieving \leq Grade 3 hemostasis. The mean of this sampling distribution will be provided as the point estimate of the proportion of activations achieving \leq Grade 3 hemostasis and the 95% confidence interval will be estimated by the lower 0.025 and upper 0.975 percentiles of this sampling distribution.

The table below demonstrates 1 iteration of this bootstrap process.

Subject ID	Observed Data Vector	Bootstrap Sampled Vector
1	(1, 1, 0, 1, 1)	(1, 0, 1, 0, 1)
2	(1, 1, 1)	(1, 1, 1)
3	(1, 0, 1, 1)	(0, 1, 1, 1)
4	(1, 1, 0, 1, 1)	(1, 1, 1, 1, 1)
5	(1, 1)	(1, 1)
...
...
N	(0, 1, 1, 0, 1)	(1, 0, 1, 1, 1)
Summary		Count the number of 1's/Total number of 1's and 0's

The above re-sampling process will then be repeated a minimum of 5000 times to estimate the sampling distribution.

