Very satisfied	xx (xx.x)	xx (xx.x)	xx (xx.x)	xx (xx.x)

Was there use of any other energy device (monopolar, traditional bipolar, advanced bipolar, ultrasonic) during the primary procedure?

Yes	xx (xx.x)	xx (xx.x)	xx (xx.x)	xx (xx.x)
No	xx (xx.x)	xx (xx.x)	xx (xx.x)	xx (xx.x)

Type of any other energy device used

None	xx (xx.x)	xx (xx.x)	xx (xx.x)	xx (xx.x)
Monopolar	xx (xx.x)	xx (xx.x)	xx (xx.x)	xx (xx.x)
Traditional bipolar	xx (xx.x)	xx (xx.x)	xx (xx.x)	xx (xx.x)
Advanced bipolar	xx (xx.x)	xx (xx.x)	xx (xx.x)	xx (xx.x)

Ultrasonic

xx (xx.x)

xx (xx.x)

xx (xx.x)

xx (xx.x)

¹ Denominator represents the corresponding usage of ENSEAL X1

Table 9
 Vessel Transection Summary – Original Procedure
 ENSEAL Analysis Set

Characteristic	Thoracic (n = xx)	Urologic (n = xx)	ENT (n = xx)	Total (n = xx)
Total Number of Vessels Transected	xx	xx	xx	xx
Hemostasis Grading Scale				
Grade 1	xx (xx.x)	xx (xx.x)	xx (xx.x)	xx (xx.x)
Grade 2	xx (xx.x)	xx (xx.x)	xx (xx.x)	xx (xx.x)
Grade 3	xx (xx.x)	xx (xx.x)	xx (xx.x)	xx (xx.x)
Grade 4	xx (xx.x)	xx (xx.x)	xx (xx.x)	xx (xx.x)
Hemostasis Achieved (Grade 3 or lower)				
Yes	xx (xx.x)	xx (xx.x)	xx (xx.x)	xx (xx.x)
95% Confidence Interval (exact method)	(xx.x, xx.x)	(xx.x, xx.x)	(xx.x, xx.x)	(xx.x, xx.x)
95% Confidence Interval (bootstrap method – sensitivity analysis)	(xx.x, xx.x)	(xx.x, xx.x)	(xx.x, xx.x)	(xx.x, xx.x)
Surgeon determination of diameter size range				
< 3 mm	xx (xx.x)	xx (xx.x)	xx (xx.x)	xx (xx.x)
3 to 5 mm	xx (xx.x)	xx (xx.x)	xx (xx.x)	xx (xx.x)
> 5 to 7 mm	xx (xx.x)	xx (xx.x)	xx (xx.x)	xx (xx.x)
Was an image captured with the vessel in an open jaw of the ENSEAL XI device perpendicular to the vessel?				
Yes	xx (xx.x)	xx (xx.x)	xx (xx.x)	xx (xx.x)
No	xx (xx.x)	xx (xx.x)	xx (xx.x)	xx (xx.x)
Determination of vessel diameter size from image				
N	xx	xx	xx	xx
Mean (SD)	xx.x (xx.x)	xx.x (xx.x)	xx.x (xx.x)	xx.x (xx.x)
Median (Min, Max)	xx.x (xx, xx)	xx.x (xx, xx)	xx.x (xx, xx)	xx.x (xx, xx)
Name of Vessel Transected				
Name 1	xx (xx.x)	xx (xx.x)	xx (xx.x)	xx (xx.x)
Name 2	xx (xx.x)	xx (xx.x)	xx (xx.x)	xx (xx.x)
Name 3	xx (xx.x)	xx (xx.x)	xx (xx.x)	xx (xx.x)
...				
Grade 3 Vessels Using Compression [3]	xx (xx.x)	xx (xx.x)	xx (xx.x)	xx (xx.x)
Grade 3 Vessels Using Monopolar Touch-up [3]	xx (xx.x)	xx (xx.x)	xx (xx.x)	xx (xx.x)

Number of Touch-up of Grade 3 Vessels Using Monopolar Device [3]

N	xx	xx	xx	xx
Mean (SD)	xx.x (xx.x)	xx.x (xx.x)	xx.x (xx.x)	xx.x (xx.x)

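### SAP 8.8's percentile bootstrap gives a zero-width interval of (100.0, 100.0) for any table column with no Grade 4 vessel, and the SAP has no fallback

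*SAP*

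**What the plan says.** SAP 8.4.1 analyses the primary endpoint by vessel: "the denominator for the primary endpoint will be the total number of vessel transections", and success is Grade 3 or lower. The main interval is exact: "An exact 95% confidence interval using the Clopper-Pearson method will be estimated". It is given for thoracic, urologic and ENT separately and pooled ("The statistics for the primary performance endpoint will be presented by procedure group and in total").

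SAP 8.8 adds a check on the independence assumption: "If the percentage of subjects with two or more vessel transections exceeds 10% a sensitivity analysis will be performed". Successes are coded 1 and Grade 4 vessels 0. For each subject, "This vector will be re-sampled with replacement to generate a bootstrap sampled vector of observations for each subject". The proportion is recomputed at least 5000 times, and "the 95% confidence interval will be estimated by the lower 0.025 and upper 0.975 percentiles of this sampling distribution".

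The Table 9 shell prints a row headed "95% Confidence Interval (bootstrap method – sensitivity analysis" for each procedure group and the total, directly below the exact interval. Tables 10.1 and 10.2 use the same format for subjects with and without prior cancer treatment. No rule covers a column with no Grade 4 vessel.

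On size, SAP section 7 gives only a floor ("providing an expected minimum of at least 35 transections within each procedure group for a total of at least 105 transections"). Neither document states an expected hemostasis rate, Grade 4 rate or number of vessels per subject.

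**The concern.** A percentile bootstrap can return only values that can be built from the observed data. If every vessel in a column is a success, no resample can contain a failure, and the method reports no uncertainty whatever the sample size. Changing the resampling unit from vessels to subjects does not cure this.

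The row exists to allow for dependence among vessels in the same subject, which should normally widen an interval. In the all-success case it would collapse to a point beside an exact interval that does not. A reader could conclude that allowing for clustering removes the uncertainty. The study tests no hypothesis and calculates no p-value, so the intervals are its only statement of precision. The columns most exposed are the procedure groups of 35 to 40 subjects and the smaller cancer-treatment columns.

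**Working it through.** **The plan's own boundary figures.** SAP section 7 takes 105 subjects and a 2% event rate. 1 − 0.98^105 = 0.880, which matches 88.0%. The exact two-sided upper limit for 0/105 is 1 − 0.025^(1/105) = 3.45%, which matches the stated figure of less than 3.5%. For a zero count in the safety data, then, the SAP does report a non-zero limit.

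**Zero Grade 4 vessels.** A column of ones resampled with replacement gives only ones, so both percentiles are 100%. A run with 35 subjects, 106 vessels and 5000 resamples gave (100.0, 100.0) when resampling vessels within subject, whole subjects and pooled vessels. The exact lower limit for n/n is 0.025^(1/n): 90.0% for 35/35, 94.9% for 70/70 and 96.5% for 105/105.

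**How often this could happen.** The Grade 4 rate p and the number of vessels m in a group are assumptions. With independent vessels, P(no Grade 4 vessel) = (1 − p)^m:

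| p | m = 35 | m = 70 | m = 105 |
|---|---|---|---|
| 1% | 70% | 49% | 35% |
| 2% | 49% | 24% | 12% |
| 3% | 34% | 12% | 4% |
| 5% | 17% | 3% | 0.5% |

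The 35-vessel column is the planning floor. With 35 subjects it means one vessel each, and such a group would not by itself trigger the bootstrap. It gets the row only if the other groups take the study past 10%.

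For at least one of three equal groups the chance is 1 − (1 − (1 − p)^m)^3. At p = 1 / 2 / 3 / 5% this is 87 / 57 / 32 / 8% for 70 vessels per group and 72 / 32 / 12 / 1% for 105.

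Dependence raises the single-group figures modestly. In a beta-binomial model with p = 2% and 35 subjects of 3 vessels each, 12% becomes 15% at an intraclass correlation (ICC) of 0.1 and 21% at 0.3.

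**One or two Grade 4 vessels, 35 subjects × 3 vessels.** The lower limit comes from the 97.5th percentile of the resampled failure count X.

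- Resampling subjects, one failure: X ~ Binomial(35, 1/35). P(X ≤ 2) = 0.922 and P(X ≤ 3) = 0.983, so the percentile is 3 and the lower limit is 1 − 3/105 = 97.1%. Clopper-Pearson for 104/105 gives 94.8%.
- Resampling subjects, two failures in different subjects: X ~ Binomial(35, 2/35). P(X ≤ 4) = 0.953 and P(X ≤ 5) = 0.987, so the limit is 1 − 5/105 = 95.2%. Clopper-Pearson for 103/105 gives 93.3%.
- Scheme as written, one failure: X ~ Binomial(3, 1/3). P(X ≤ 2) = 26/27 = 0.963, so the percentile is 3 and the limit is again 97.1%.
- Scheme as written, two failures in different subjects: X ~ Binomial(6, 1/3). P(X ≤ 3) = 0.900 and P(X ≤ 4) = 0.982, so the limit is 1 − 4/105 = 96.2%.

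**Coverage.** An interval of (100, 100) misses any true rate below 100%, so bootstrap coverage cannot exceed 1 − P(no Grade 4 vessel). At p = 1% and 70 independent vessels that ceiling is 51%. Simulation used 35 subjects, 2 or 3 vessels each, p from 1% to 3%, and ICC 0 or 0.2. Coverage of the nominal 95% interval ran from just under 50% to just under 90% for the subject bootstrap, and from about 40% to just under 90% for the scheme as written. Vessel-level Clopper-Pearson covered about 95% to 99.6%.

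**The case against.** The strongest reply is that little rests on this row. The exact interval is primary and sits directly above the bootstrap row, together with the Grade 1 to 4 counts. A reader would see 70/70 and (94.9, 100.0) beside (100.0, 100.0) and could discount the second. No decision depends on either, SAP 8.9 calls the cancer-treatment tables exploratory, and the SAP nowhere calls the bootstrap the more cautious interval. All of this stands and limits the harm.

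A reader might infer that an all-success group is the likely result because success includes Grade 3. The documents do not support that. They give no rate and no vessel count, and SAP 8.4.1 expects several vessels per subject, which moves the relevant columns of the table away from 35. At a 5% Grade 4 rate the event is rare by 70 vessels. It is plausible at rates near 1%, and no more can be said.

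The near-boundary gaps are also moderate: at 105 vessels the subject bootstrap's lower limit is 2.3 points too high with one failure and 1.9 with two, measured against Clopper-Pearson.

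Finally, data with no failures carry no information about within-subject dependence, so any clustered interval there rests on a convention. That is correct, and the convention must be labelled. A footnote alone would deal with the zero-failure column but not with the narrow intervals at one or two failures.

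**Conclusion.** Wrong as written. Any column of Table 9, 10.1 or 10.2 with no Grade 4 vessel gets a bootstrap interval of (100.0, 100.0) when the row is produced, whichever unit is resampled, and the SAP does not say what to do. This part is exact and needs no assumption.

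How often it would occur is an assumption: from 3% to 49% per group at 70 vessels and 0.5% to 35% at 105, for Grade 4 rates of 5% down to 1% and independent vessels, and modestly higher with dependence. With one or two failures the row still understates uncertainty relative to the exact interval it is meant to check.

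It would be tempting to conclude that the primary result is compromised. It is not, because the Clopper-Pearson interval does not depend on the bootstrap. The damage is confined to a misleading sensitivity row, but the remedy is cheap enough that the row should not be left as it is.

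**What to change.** In SAP 8.8 and Tables 9, 10.1 and 10.2, replace the percentile bootstrap with a clustered interval that is valid near 100%. A suitable choice is Clopper-Pearson evaluated at the effective sample size (Korn-Graubard): the number of vessels divided by the estimated design effect for subjects as clusters, capped at the number of vessels.

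When a column has no Grade 4 vessel the design effect cannot be estimated. Use the number of subjects as the effective size and label the result a conservative bound, since it assumes complete dependence within subject. For 35 subjects the lower limit is 90.0%.

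If the bootstrap row is kept, print 'not estimable' in columns with no Grade 4 vessel. A wider suppression rule, such as fewer than five Grade 4 vessels, is not advised: at Grade 4 rates of 3 / 2 / 1% it would remove the row from 79 / 94 / 99.6% of 105-vessel groups.

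The cost is SAP wording and code, with no new data. Intervals near 100% become wider.

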8.9 Subgroup Analysis

Subgroup analyses are planned to be performed for vessel transection variables collected through the vessel transected form, Grade 3 form, and Grade 4 form for the subjects who had medical history of treatment for cancer (yes or no) by procedure groups and all groups combined. Subjects who had a medical history of treatment for cancer is identified through the treatment history form and those who checked for “Neoadjuvant chemotherapy” or “Neoadjuvant radiation therapy” boxes. These analyses will be exploratory and summary statistics for the procedure-related parameters will be provided for each subgroup.

8.10 Assessment of Site Homogeneity

No summaries or adjustments by study site are planned for this study.

9 Data Monitoring Committee (DMC)

No Data Monitoring Committee was planned or utilized during this study.

Appendix: Table Shells and List of Listings to be Generated

Table shells are provided below for all summaries to be generated for this study. These shells are a guide to the general layout of data to be presented. Minor modifications can be made to suit existing programs or macros that are available. Additionally, a list of all listings to be created is provided corresponding to the eCRFs that are used in this study. All fields collected will be listed.

Table 1
Subject Disposition
All Subjects

	Thoracic n (%)	Urologic n (%)	ENT n (%)	Total n (%)
Signed Informed Consent				xx
Screen Failure				xx
Preoperative/Preprocedural				xx
Intraoperative/Intraprocedural				xx
ENSEAL Analysis Set	xx	xx	xx	xx
Completed the Study	xx (xx.x)	xx (xx.x)	xx (xx.x)	xx (xx.x)
Discontinued from the Study	xx (xx.x)	xx (xx.x)	xx (xx.x)	xx (xx.x)
Reason for Discontinuation				
Adverse Event	xx (xx.x)	xx (xx.x)	xx (xx.x)	xx (xx.x)
Death	xx (xx.x)	xx (xx.x)	xx (xx.x)	xx (xx.x)
Lost to Follow-up	xx (xx.x)	xx (xx.x)	xx (xx.x)	xx (xx.x)
Physician Decision	xx (xx.x)	xx (xx.x)	xx (xx.x)	xx (xx.x)
Site or Study Termination	xx (xx.x)	xx (xx.x)	xx (xx.x)	xx (xx.x)
Withdrawal by Subject	xx (xx.x)	xx (xx.x)	xx (xx.x)	xx (xx.x)
Other	xx (xx.x)	xx (xx.x)	xx (xx.x)	xx (xx.x)

All percentages are calculated using the number of subjects in the ENSEAL Analysis Set as the denominator.

Programming note: Only categories actually observed in the database need to be displayed for Reason for Discontinuation.

Table 2
 Subject Demographics and Vital Signs
 ENSEAL Analysis Set

Characteristic	Thoracic (N = xx)	Urologic (N = xx)	ENT (N = xx)	Total (N = xx)
Age at Consent (yrs)				
n	xx	xx	xx	xx
Mean (SD)	xx.x (xx.x)	xx.x (xx.x)	xx.x (xx.x)	xx.x (xx.x)
Median (Min, Max)	xx.x (xx, xx)	xx.x (xx, xx)	xx.x (xx, xx)	xx.x (xx, xx)
Gender, n (%)				
Male	xx (xx.x)	xx (xx.x)	xx (xx.x)	xx (xx.x)
Female	xx (xx.x)	xx (xx.x)	xx (xx.x)	xx (xx.x)
Ethnicity, n (%)				
Hispanic or Latino	xx (xx.x)	xx (xx.x)	xx (xx.x)	xx (xx.x)
Not Hispanic or Latino	xx (xx.x)	xx (xx.x)	xx (xx.x)	xx (xx.x)
Not Reported	xx (xx.x)	xx (xx.x)	xx (xx.x)	xx (xx.x)
Race, n (%)				
Race 1	xx (xx.x)	xx (xx.x)	xx (xx.x)	xx (xx.x)
.....	xx (xx.x)	xx (xx.x)	xx (xx.x)	xx (xx.x)
Childbearing Potential, if female, n (%)				
Of childbearing potential	xx (xx.x)	xx (xx.x)	xx (xx.x)	xx (xx.x)
Permanently sterilized	xx (xx.x)	xx (xx.x)	xx (xx.x)	xx (xx.x)
Postmenopausal	xx (xx.x)	xx (xx.x)	xx (xx.x)	xx (xx.x)
Height (cm)				
n	xx	xx	xx	xx
Mean (SD)	xx.x (xx.x)	xx.x (xx.x)	xx.x (xx.x)	xx.x (xx.x)
Median (Min, Max)	xx.x (xx, xx)	xx.x (xx, xx)	xx.x (xx, xx)	xx.x (xx, xx)
Weight (kg)				
n	xx	xx	xx	xx
Mean (SD)	xx.x (xx.x)	xx.x (xx.x)	xx.x (xx.x)	xx.x (xx.x)
Median (Min, Max)	xx.x (xx, xx)	xx.x (xx, xx)	xx.x (xx, xx)	xx.x (xx, xx)
Body Mass Index (kg/m^2)				
n	xx	xx	xx	xx
Mean (SD)	xx.x (xx.x)	xx.x (xx.x)	xx.x (xx.x)	xx.x (xx.x)
Median (Min, Max)	xx.x (xx.x)	xx.x (xx.x)	xx.x (xx.x)	xx.x (xx.x)

Denominator and percentages are based on subjects with non-missing data. For child-bearing potential, denominator is number of females in each group.

Table 3
Medical History by System Organ Class and Preferred Term
ENSEAL Analysis Set

System Organ Class	Preferred Term	Thoracic n (%)	Urologic n (%)	ENT n (%)	Total n (%)
Total		xx (xx.x)	xx (xx.x)	xx (xx.x)	xx (xx.x)
System Organ Class 1		xx (xx.x)	xx (xx.x)	xx (xx.x)	xx (xx.x)
	Preferred Term 1	xx (xx.x)	xx (xx.x)	xx (xx.x)	xx (xx.x)
	Preferred Term 2	xx (xx.x)	xx (xx.x)	xx (xx.x)	xx (xx.x)
	Preferred Term 3	xx (xx.x)	xx (xx.x)	xx (xx.x)	xx (xx.x)
System Organ Class 2		xx (xx.x)	xx (xx.x)	xx (xx.x)	xx (xx.x)
	Preferred Term 1	xx (xx.x)	xx (xx.x)	xx (xx.x)	xx (xx.x)
	Preferred Term 2	xx (xx.x)	xx (xx.x)	xx (xx.x)	xx (xx.x)
System Organ Class 3		xx (xx.x)	xx (xx.x)	xx (xx.x)	xx (xx.x)
	Preferred Term 1	xx (xx.x)	xx (xx.x)	xx (xx.x)	xx (xx.x)
	Preferred Term 2	xx (xx.x)	xx (xx.x)	xx (xx.x)	xx (xx.x)
	Preferred Term 3	xx (xx.x)	xx (xx.x)	xx (xx.x)	xx (xx.x)
System Organ Class 4		xx (xx.x)	xx (xx.x)	xx (xx.x)	xx (xx.x)
	Preferred Term 1	xx (xx.x)	xx (xx.x)	xx (xx.x)	xx (xx.x)
	Preferred Term 2	xx (xx.x)	xx (xx.x)	xx (xx.x)	xx (xx.x)

Table 4.1
Background Information – Thoracic Procedure Group
ENSEAL Analysis Set

Characteristic	Thoracic n (%)
Primary Indication for the Procedure	
Lung resection (branches, no PA/PV)	xx (xx.x)
Other	xx (xx.x)
Specific Procedure Performed	
Lung carcinoma	xx (xx.x)
Emphysema	xx (xx.x)
Lung infection (TBC, aspergillosis, bacterial)	xx (xx.x)
Other	xx (xx.x)

Programming note: Only categories actually observed in the database need to be displayed.

Table 4.2
Background Information – Urologic Procedure Group
ENSEAL Analysis Set

Characteristic	Urologic n (%)
Primary Indication for the Procedure	
Partial Nephrectomy	xx (xx.x)
Nephrectomy	xx (xx.x)
Radical prostatectomy	xx (xx.x)
Cystectomy	xx (xx.x)
Adrenalectomy	xx (xx.x)
Other	xx (xx.x)
Specific Procedure Performed	
Partial Nephrectomy primary indication	
Benign disease suspicion	xx (xx.x)
Bilateral tumors	xx (xx.x)
Cystic nephroma	xx (xx.x)
Solitary kidney	xx (xx.x)
Complex cyst	xx (xx.x)
Von Hippel-Lindau disease	xx (xx.x)
Bourneville syndrome	xx (xx.x)
Angiomyolipoma	xx (xx.x)
Familial RCC	xx (xx.x)
Oncocytoma	xx (xx.x)
Graft kidney	xx (xx.x)
Lithiasis	xx (xx.x)
Arterial stenosis	xx (xx.x)
Borderline renal function	xx (xx.x)
Chronic pyelonephritis	xx (xx.x)
Hypertension/diabetes	xx (xx.x)
Nephrectomy primary indication	
Renal cancer	xx (xx.x)
Severe renal trauma	xx (xx.x)
Symptomatic hydronephrosis	xx (xx.x)
Chronic infection	xx (xx.x)
Polycystic kidney disease	xx (xx.x)
Shrunken kidney	xx (xx.x)
Hypertension	xx (xx.x)
Renal calculus	xx (xx.x)
Other	xx (xx.x)

Radical prostatectomy primary indication	
Prostate cancer	xx (xx.x)
Other	xx (xx.x)
Cystectomy primary indication	
Bladder cancer	xx (xx.x)
Other	xx (xx.x)
Adrenalectomy primary indication	
Malignancy suspicion or malignant tumors	xx (xx.x)
Non-functional tumors with the risk of malignancy	xx (xx.x)
Functional adrenal tumors	xx (xx.x)
Other	xx (xx.x)
Other indication	xx (xx.x)

Programming note: Only categories actually observed in the database need to be displayed.

Table 4.3
Background Information – ENT Procedure Group
ENSEAL Analysis Set

Characteristic	ENT n (%)
Primary Indication for the Procedure	
Thyroidectomy	xx (xx.x)
Tonsillectomy	xx (xx.x)
Parotidectomy	xx (xx.x)
Adenoidectomy	xx (xx.x)
Radical neck dissection	xx (xx.x)
Other	xx (xx.x)
Specific Procedure Performed	
Thyroidectomy primary indication	
Thyroid cancer	xx (xx.x)
Goiter	xx (xx.x)
Hyperthyroidism	xx (xx.x)
Indeterminate or suspicious thyroid nodules	xx (xx.x)
Other	xx (xx.x)
Tonsillectomy primary indication	
Adenotonsillar hyperplasia with obstructive sleep apnea, failure to thrive, or abnormal dentofacial growth	xx (xx.x)
Suspicion of malignant disease	xx (xx.x)
Hemorrhagic tonsillitis	xx (xx.x)
Adenotonsillar hyperplasia with upper airway obstruction, dysphagia, or speech impairment, and halitosis	xx (xx.x)
Recurrent or chronic pharyngotonsillitis	xx (xx.x)
Peritonsillar abscess	xx (xx.x)
Streptococcal carriage	xx (xx.x)
Other	xx (xx.x)
Parotidectomy primary indication	
Malignant tumors	xx (xx.x)
Benign tumors	xx (xx.x)
Inflammatory conditions (chronic parotitis, deep salivary calculi, or parotid abscess)	xx (xx.x)

Salivary duct stones	
Sialorrhea	xx (xx.x)
Other	xx (xx.x)
Radical neck dissection primary indication	
Head and neck cancer	xx (xx.x)
Other	xx (xx.x)
Adenoidectomy primary indication	
Adenotonsillar hyperplasia with obstructive sleep apnea, failure to thrive, or abnormal dentofacial growth	xx (xx.x)
Suspicion of malignant disease	xx (xx.x)
Adenotonsillar hyperplasia with upper airway obstruction, dysphagia, or speech impairment, and halitosis	xx (xx.x)
Otitis media	xx (xx.x)
Recurrent or chronic rhinosinusitis or adenoiditis	xx (xx.x)
Other	xx (xx.x)
Other indication	xx (xx.x)

Programming note: Only categories actually observed in the database need to be displayed.

Table 5
 Additional Background Information
 ENSEAL Analysis Set

Characteristic	Thoracic (n = xx)	Urologic (n = xx)	ENT (n = xx)	Total (n = xx)
Current Smoking Status, n (%)				
Current smoker	xx (xx.x)	xx (xx.x)	xx (xx.x)	xx (xx.x)
Former smoker	xx (xx.x)	xx (xx.x)	xx (xx.x)	xx (xx.x)
Never smoked	xx (xx.x)	xx (xx.x)	xx (xx.x)	xx (xx.x)
Years Since Stopped Smoking				
n	xx	xx	xx	xx
Mean (SD)	xx (xx.x)	xx (xx.x)	xx (xx.x)	xx (xx.x)
Median (Min, Max)	xx.x (xx, xx)	xx.x (xx, xx)	xx.x (xx, xx)	xx.x (xx, xx)
ASA Score, n (%)				
Completely healthy fit	xx (xx.x)	xx (xx.x)	xx (xx.x)	xx (xx.x)
Mild systemic disease	xx (xx.x)	xx (xx.x)	xx (xx.x)	xx (xx.x)
Severe systemic disease not incapacitating	xx (xx.x)	xx (xx.x)	xx (xx.x)	xx (xx.x)
Severe systemic disease that is a constant threat to life	xx (xx.x)	xx (xx.x)	xx (xx.x)	xx (xx.x)
Moribund patient who is not expected to survive	xx (xx.x)	xx (xx.x)	xx (xx.x)	xx (xx.x)

Table 6
Treatment History
ENSEAL Analysis Set

Characteristic	Thoracic n (%)	Urologic n (%)	ENT n (%)	Total n (%)
Is the Indication for the Subject's Surgery Due to a Cancer Diagnosis?				
Yes	xx (xx.x)	xx (xx.x)	xx (xx.x)	xx (xx.x)
No	xx (xx.x)	xx (xx.x)	xx (xx.x)	xx (xx.x)
Type of treatment within 90 days prior to surgery ¹				
None	xx (xx.x)	xx (xx.x)	xx (xx.x)	xx (xx.x)
Observation	xx (xx.x)	xx (xx.x)	xx (xx.x)	xx (xx.x)
Neoadjuvant chemotherapy	xx (xx.x)	xx (xx.x)	xx (xx.x)	xx (xx.x)
Neoadjuvant radiation therapy	xx (xx.x)	xx (xx.x)	xx (xx.x)	xx (xx.x)

1 Cumulative percentage may exceed 100 as multiple responses are recorded

2 Denominator represents patients receiving neoadjuvant chemotherapy or neoadjuvant radiation therapy

Table 7
 Intra-Operative and Post-Operative Information
 ENSEAL Analysis Set

Characteristic	Thoracic n (%)	Urologic n (%)	ENT n (%)	Total n (%)
Occurrence of Vessel Skeletonization?				
Yes	xx (xx.x)	xx (xx.x)	xx (xx.x)	xx (xx.x)
No	xx (xx.x)	xx (xx.x)	xx (xx.x)	xx (xx.x)
Was there prophylactic use of clips or sutures as standard of surgical care before vessel transection?				
Yes	xx (xx.x)	xx (xx.x)	xx (xx.x)	xx (xx.x)
No	xx (xx.x)	xx (xx.x)	xx (xx.x)	xx (xx.x)
Presence of Inflamed Tissue or Calcified Tissues/Vessels				
Yes	xx (xx.x)	xx (xx.x)	xx (xx.x)	xx (xx.x)
No	xx (xx.x)	xx (xx.x)	xx (xx.x)	xx (xx.x)
Presence of Calcified Tissues/Vessels				
Yes	xx (xx.x)	xx (xx.x)	xx (xx.x)	xx (xx.x)
No	xx (xx.x)	xx (xx.x)	xx (xx.x)	xx (xx.x)
Presence of Atherosclerotic Tissue				
Yes	xx (xx.x)	xx (xx.x)	xx (xx.x)	xx (xx.x)
No	xx (xx.x)	xx (xx.x)	xx (xx.x)	xx (xx.x)
Presence of Fibrotic Tissue				
Yes	xx (xx.x)	xx (xx.x)	xx (xx.x)	xx (xx.x)
No	xx (xx.x)	xx (xx.x)	xx (xx.x)	xx (xx.x)
Presence of Adhesions				
Yes	xx (xx.x)	xx (xx.x)	xx (xx.x)	xx (xx.x)
No	xx (xx.x)	xx (xx.x)	xx (xx.x)	xx (xx.x)
Was an Ethicon trocar used with ENSEAL X1 (if applicable)?				
Yes	xx (xx.x)	xx (xx.x)	xx (xx.x)	xx (xx.x)
No	xx (xx.x)	xx (xx.x)	xx (xx.x)	xx (xx.x)
Surgical Approach				
Open	xx (xx.x)	xx (xx.x)	xx (xx.x)	xx (xx.x)
Laparoscopic	xx (xx.x)	xx (xx.x)	xx (xx.x)	xx (xx.x)

Conversion to Open

Yes
No

xx (xx.x) xx (xx.x) xx (xx.x) xx (xx.x)
xx (xx.x) xx (xx.x) xx (xx.x) xx (xx.x)

Was ENSEAL X1 Used for Tissue Cutting or Dissection?

Yes
No

xx (xx.x) xx (xx.x) xx (xx.x) xx (xx.x)
xx (xx.x) xx (xx.x) xx (xx.x) xx (xx.x)

Procedure Duration (hours)

N
Mean (SD)
Median (Min, Max)

xx xx xx xx
xx.x (xx.x) xx.x (xx.x) xx.x (xx.x) xx.x (xx.x)
xx.x (xx, xx) xx.x (xx, xx) xx.x (xx, xx) xx.x (xx, xx)

Procedure Duration (hours)

N
Mean (SD)
Median (Min, Max)

xx xx xx xx
xx.x (xx.x) xx.x (xx.x) xx.x (xx.x) xx.x (xx.x)
xx.x (xx, xx) xx.x (xx, xx) xx.x (xx, xx) xx.x (xx, xx)

Volume of Estimated Intra-operative Blood Loss (mL)

N
Mean (SD)
Median (Min, Max)

xx xx xx xx
xx.x (xx.x) xx.x (xx.x) xx.x (xx.x) xx.x (xx.x)
xx.x (xx, xx) xx.x (xx, xx) xx.x (xx, xx) xx.x (xx, xx)

Table 8
 ENSEAL X1 Usage
 ENSEAL Analysis Set

Characteristic	Thoracic n (%)	Urologic n (%)	ENT n (%)	Total n (%)
Were adhesions removed or divided by ENSEAL X1?				
Yes	xx (xx.x)	xx (xx.x)	xx (xx.x)	xx (xx.x)
No	xx (xx.x)	xx (xx.x)	xx (xx.x)	xx (xx.x)
Surgeon's satisfaction with the adhesion removal or division by ENSEAL X1 ¹				
Very dissatisfied	xx (xx.x)	xx (xx.x)	xx (xx.x)	xx (xx.x)
Dissatisfied	xx (xx.x)	xx (xx.x)	xx (xx.x)	xx (xx.x)
Neither Satisfied or Dissatisfied	xx (xx.x)	xx (xx.x)	xx (xx.x)	xx (xx.x)
Satisfied	xx (xx.x)	xx (xx.x)	xx (xx.x)	xx (xx.x)
Very satisfied	xx (xx.x)	xx (xx.x)	xx (xx.x)	xx (xx.x)
Were lymphatics bundles divided by ENSEAL X1?				
Yes	xx (xx.x)	xx (xx.x)	xx (xx.x)	xx (xx.x)
No	xx (xx.x)	xx (xx.x)	xx (xx.x)	xx (xx.x)
Surgeon's satisfaction with the lymphatics bundles divide by ENSEAL X1 ¹				
Very dissatisfied	xx (xx.x)	xx (xx.x)	xx (xx.x)	xx (xx.x)
Dissatisfied	xx (xx.x)	xx (xx.x)	xx (xx.x)	xx (xx.x)
Neither Satisfied or Dissatisfied	xx (xx.x)	xx (xx.x)	xx (xx.x)	xx (xx.x)
Satisfied	xx (xx.x)	xx (xx.x)	xx (xx.x)	xx (xx.x)
Very satisfied	xx (xx.x)	xx (xx.x)	xx (xx.x)	xx (xx.x)
Were tissue bundles divided by ENSEAL X1				
Yes	xx (xx.x)	xx (xx.x)	xx (xx.x)	xx (xx.x)
No	xx (xx.x)	xx (xx.x)	xx (xx.x)	xx (xx.x)
Surgeon's satisfaction with the tissue bundle divide by ENSEAL X1 ¹				
Very dissatisfied	xx (xx.x)	xx (xx.x)	xx (xx.x)	xx (xx.x)
Dissatisfied	xx (xx.x)	xx (xx.x)	xx (xx.x)	xx (xx.x)
Neither Satisfied or Dissatisfied	xx (xx.x)	xx (xx.x)	xx (xx.x)	xx (xx.x)
Satisfied	xx (xx.x)	xx (xx.x)	xx (xx.x)	xx (xx.x)
Very satisfied	xx (xx.x)	xx (xx.x)	xx (xx.x)	xx (xx.x)
Was the ENSEAL X1 used for tissue grasping?				

Yes	xx (xx.x)	xx (xx.x)	xx (xx.x)	xx (xx.x)
No	xx (xx.x)	xx (xx.x)	xx (xx.x)	xx (xx.x)

Surgeon's satisfaction with the tissue grasping by ENSEAL X1?¹

Very dissatisfied	xx (xx.x)	xx (xx.x)	xx (xx.x)	xx (xx.x)
Dissatisfied	xx (xx.x)	xx (xx.x)	xx (xx.x)	xx (xx.x)
Neither Satisfied or Dissatisfied	xx (xx.x)	xx (xx.x)	xx (xx.x)	xx (xx.x)
Satisfied	xx (xx.x)	xx (xx.x)	xx (xx.x)	xx (xx.x)
Very satisfied	xx (xx.x)	xx (xx.x)	xx (xx.x)	xx (xx.x)

Was the ENSEAL X1 used for tissue cutting?

Yes	xx (xx.x)	xx (xx.x)	xx (xx.x)	xx (xx.x)
No	xx (xx.x)	xx (xx.x)	xx (xx.x)	xx (xx.x)

Surgeon's satisfaction with the tissue cutting by ENSEAL X1?¹

Very dissatisfied	xx (xx.x)	xx (xx.x)	xx (xx.x)	xx (xx.x)
Dissatisfied	xx (xx.x)	xx (xx.x)	xx (xx.x)	xx (xx.x)
Neither Satisfied or Dissatisfied	xx (xx.x)	xx (xx.x)	xx (xx.x)	xx (xx.x)
Satisfied	xx (xx.x)	xx (xx.x)	xx (xx.x)	xx (xx.x)
Very satisfied	xx (xx.x)	xx (xx.x)	xx (xx.x)	xx (xx.x)

Was the ENSEAL X1 used for tissue dissection?

Yes	xx (xx.x)	xx (xx.x)	xx (xx.x)	xx (xx.x)
No	xx (xx.x)	xx (xx.x)	xx (xx.x)	xx (xx.x)

Surgeon's satisfaction with the tissue dissection by ENSEAL X1?¹

Very dissatisfied	xx (xx.x)	xx (xx.x)	xx (xx.x)	xx (xx.x)
Dissatisfied	xx (xx.x)	xx (xx.x)	xx (xx.x)	xx (xx.x)
Neither Satisfied or Dissatisfied	xx (xx.x)	xx (xx.x)	xx (xx.x)	xx (xx.x)
Satisfied	xx (xx.x)	xx (xx.x)	xx (xx.x)	xx (xx.x)
Very satisfied	xx (xx.x)	xx (xx.x)	xx (xx.x)	xx (xx.x)

Was there use of any other energy device (monopolar, traditional bipolar, advanced bipolar, ultrasonic) during the primary procedure?

Yes	xx (xx.x)	xx (xx.x)	xx (xx.x)	xx (xx.x)
No	xx (xx.x)	xx (xx.x)	xx (xx.x)	xx (xx.x)

Type of any other energy device used

None	xx (xx.x)	xx (xx.x)	xx (xx.x)	xx (xx.x)
Monopolar	xx (xx.x)	xx (xx.x)	xx (xx.x)	xx (xx.x)
Traditional bipolar	xx (xx.x)	xx (xx.x)	xx (xx.x)	xx (xx.x)
Advanced bipolar	xx (xx.x)	xx (xx.x)	xx (xx.x)	xx (xx.x)

Ultrasonic

xx (xx.x)

xx (xx.x)

xx (xx.x)

xx (xx.x)

¹ Denominator represents the corresponding usage of ENSEAL X1

Table 9
 Vessel Transection Summary – Original Procedure
 ENSEAL Analysis Set

Characteristic	Thoracic (n = xx)	Urologic (n = xx)	ENT (n = xx)	Total (n = xx)
Total Number of Vessels Transected	xx	xx	xx	xx
Hemostasis Grading Scale				
Grade 1	xx (xx.x)	xx (xx.x)	xx (xx.x)	xx (xx.x)
Grade 2	xx (xx.x)	xx (xx.x)	xx (xx.x)	xx (xx.x)
Grade 3	xx (xx.x)	xx (xx.x)	xx (xx.x)	xx (xx.x)
Grade 4	xx (xx.x)	xx (xx.x)	xx (xx.x)	xx (xx.x)
Hemostasis Achieved (Grade 3 or lower)				
Yes	xx (xx.x)	xx (xx.x)	xx (xx.x)	xx (xx.x)
95% Confidence Interval (exact method)	(xx.x, xx.x)	(xx.x, xx.x)	(xx.x, xx.x)	(xx.x, xx.x)
95% Confidence Interval (bootstrap method – sensitivity analysis)	(xx.x, xx.x)	(xx.x, xx.x)	(xx.x, xx.x)	(xx.x, xx.x)
Surgeon determination of diameter size range				
< 3 mm	xx (xx.x)	xx (xx.x)	xx (xx.x)	xx (xx.x)
3 to 5 mm	xx (xx.x)	xx (xx.x)	xx (xx.x)	xx (xx.x)
> 5 to 7 mm	xx (xx.x)	xx (xx.x)	xx (xx.x)	xx (xx.x)
Was an image captured with the vessel in an open jaw of the ENSEAL XI device perpendicular to the vessel?				
Yes	xx (xx.x)	xx (xx.x)	xx (xx.x)	xx (xx.x)
No	xx (xx.x)	xx (xx.x)	xx (xx.x)	xx (xx.x)
Determination of vessel diameter size from image				
N	xx	xx	xx	xx
Mean (SD)	xx.x (xx.x)	xx.x (xx.x)	xx.x (xx.x)	xx.x (xx.x)
Median (Min, Max)	xx.x (xx, xx)	xx.x (xx, xx)	xx.x (xx, xx)	xx.x (xx, xx)
Name of Vessel Transected				
Name 1	xx (xx.x)	xx (xx.x)	xx (xx.x)	xx (xx.x)
Name 2	xx (xx.x)	xx (xx.x)	xx (xx.x)	xx (xx.x)
Name 3	xx (xx.x)	xx (xx.x)	xx (xx.x)	xx (xx.x)
...				
Grade 3 Vessels Using Compression [3]	xx (xx.x)	xx (xx.x)	xx (xx.x)	xx (xx.x)
Grade 3 Vessels Using Monopolar Touch-up [3]	xx (xx.x)	xx (xx.x)	xx (xx.x)	xx (xx.x)

Number of Touch-up of Grade 3 Vessels Using Monopolar Device [3]

N	xx	xx	xx	xx
Mean (SD)	xx.x (xx.x)	xx.x (xx.x)	xx.x (xx.x)	xx.x (xx.x)
Median (Min, Max)	xx.x (xx, xx)	xx.x (xx, xx)	xx.x (xx, xx)	xx.x (xx, xx)

Grade 3 Vessels Using Bipolar Touch-ups [3]

xx (xx.x)	xx (xx.x)	xx (xx.x)	xx (xx.x)
-----------	-----------	-----------	-----------

Number of Touch-up of Grade 3 Vessels Using Bipolar Device [3]

N	xx	xx	xx	xx
Mean (SD)	xx.x (xx.x)	xx.x (xx.x)	xx.x (xx.x)	xx.x (xx.x)
Median (Min, Max)	xx.x (xx, xx)	xx.x (xx, xx)	xx.x (xx, xx)	xx.x (xx, xx)

Grade 3 Vessels Using ENSEAL X1 Touch-up [3]

xx (xx.x)	xx (xx.x)	xx (xx.x)	xx (xx.x)
-----------	-----------	-----------	-----------

Number of ENSEAL X1 Touch-ups of Grade 3 Vessels [3]

N	xx	xx	xx	xx
Mean (SD)	xx.x (xx.x)	xx.x (xx.x)	xx.x (xx.x)	xx.x (xx.x)
Median (Min, Max)	xx.x (xx, xx)	xx.x (xx, xx)	xx.x (xx, xx)	xx.x (xx, xx)

Vessels transected as Grade 4 [4]

xx (xx.x)	xx (xx.x)	xx (xx.x)	xx (xx.x)
-----------	-----------	-----------	-----------

Name of Vessel Transected as Grade 4 [4]

Name 1	xx (xx.x)	xx (xx.x)	xx (xx.x)	xx (xx.x)
Name 2	xx (xx.x)	xx (xx.x)	xx (xx.x)	xx (xx.x)
Name 3	xx (xx.x)	xx (xx.x)	xx (xx.x)	xx (xx.x)
...				

Number of Additional Hemostatic Measure Used to Obtain Hemostasis for

Grade 4 Vessels [4]

N	xx	xx	xx	xx
Mean (SD)	xx.x (xx.x)	xx.x (xx.x)	xx.x (xx.x)	xx.x (xx.x)
Median (Min, Max)	xx.x (xx, xx)	xx.x (xx, xx)	xx.x (xx, xx)	xx.x (xx, xx)

Type of additional hemostatic measure(s) used to obtain hemostasis for

Grade 4 Vessels [2]

Hemoclips	xx (xx.x)	xx (xx.x)	xx (xx.x)	xx (xx.x)
Staples	xx (xx.x)	xx (xx.x)	xx (xx.x)	xx (xx.x)
Sutures	xx (xx.x)	xx (xx.x)	xx (xx.x)	xx (xx.x)
Fibrin Sealants	xx (xx.x)	xx (xx.x)	xx (xx.x)	xx (xx.x)
Adjuactive Topical Hemostats (except Fibrin Sealants)	xx (xx.x)	xx (xx.x)	xx (xx.x)	xx (xx.x)
Other advanced energy products	xx (xx.x)	xx (xx.x)	xx (xx.x)	xx (xx.x)
Other	xx (xx.x)	xx (xx.x)	xx (xx.x)	xx (xx.x)

1 Denominator and percentages are based on number of vessels transected in each group.

2 Multiple responses are collected

3 The denominator is number of Grade 3 vessel transections

4 The denominator is number of Grade 4 vessel transections

Programming notes:

1. Only records indicated as “Original procedure” will be summarized in this table.
2. For number of vessels using touch up questions, the number presented will be the number of times “yes” is answered to the corresponding CRF question (VTMONO or VTENS); For summary statistics on number of touch-ups, the variables VTTUP and VTTUPS will be summarized

The following tables will have the same format as Table 9:

